## 1.3. Study Rationale

In nonclinical studies, the fact that U3-1402 binds specifically to the HER3 extracellular domain (ECD) and does not bind to other HER family proteins has been confirmed. In vivo studies indicate that U3-1402 exhibits HER3 expression-dependent cell growth inhibition activity, moreover, no growth inhibition was observed in HER3-negative cells, thus confirming the HER3 specificity of U3-1402. U3-1402 showed significant tumor regression in human breast cancer xenograft models.

In summary, U3-1402 is hypothesized to show anticancer activity with a manageable safety profile in HER3-positive cancer.

High HER3 expression was reported in breast cancer patients.  Therefore, U3-1402 is being developed as an ADC targeting HER3-positive breast cancer, NSCLC and potentially other solid tumors expressing HER3.

# 1.4. Risks and Benefits for Study Subjects

U3-1402 is being developed for the treatment of HER3-expressing malignant tumors. The product is in the early stages of development.

Nonclinical studies have demonstrated the antitumor activity of U3-1402 in HER3 tumor-bearing mouse models. Thus, U3-1402 is hypothesized to demonstrate efficacy in HER3-expressing tumors in patients.

In nonclinical toxicology studies, toxicity of intestinal, lymphatic/hematopoietic, skin, pulmonary, reproductive and accessory organ, hepatic, cardiovascular, and renal systems were

found in association with the administration of U3-1402. As with any therapeutic antibodies, there is a possibility of infusion-related reactions and immune responses causing allergic or anaphylactic reactions to U3-1402. Considering the toxicity data from the nonclinical studies, the potential risks of QT prolongation, left ventricular ejection fraction (LVEF) decreased, potential Hy's Law, ILD, pneumonitis, infusion-related reaction, dry eye, keratitis, photosensitivity, stomatitis, alopecia, dry skin, rash, rash maculopapular, and skin pigmentation in humans from exposure to U3-1402 have been closely monitored and evaluated in the U3-1402 clinical development program.

Based on the preliminary clinical safety data from the ongoing U3-1402 studies, nausea, decreased appetite, platelet count decreased/thrombocytopenia, white blood cell count decreased/leukopenia, neutrophil count decreased/neutropenia, vomiting, anemia, diarrhea and interstitial lung disease/pneumonitis are identified risks and will continue to be closely monitored and evaluated in the U3-1402 clinical development program.

In conclusion, based on the efficacy and safety data from the nonclinical studies and the preliminary clinical efficacy and safety data from the ongoing studies, the benefit/risk balance supports continued clinical development of U3-1402.

## 2. STUDY OBJECTIVES AND HYPOTHESIS

# 2.1. Study Objectives

### 2.1.1. Primary Objectives

#### 2.1.1.1. Dose Escalation Part

The primary objectives are as follows:

- 1. To assess safety and tolerability of U3-1402.
- 2. To determine the maximum tolerated dose (MTD) of U3-1402.

### 2.1.1.2. Dose Finding Part

The primary objectives are as follows:

- 1. To assess safety and evaluate efficacy of U3-1402.
- 2. To assess safety of alternative dosing schedule(s) of U3-1402.
- 3. To determine the recommended dose(s) for expansion (RDEs) of U3-1402.

#### 2.1.1.3. Dose Expansion Part

The primary objective is as follows:

1. To assess safety and evaluate efficacy of U3-1402 at the RDEs in subjects with HER3-positive, HER2-negative (including HR-positive and TNBC) advanced/unresectable or metastatic breast cancers.

### 2.1.2. Secondary Objectives

#### 2.1.2.1. Dose Escalation Part

The secondary objectives are as follows:

- 1. To assess the PK profiles of U3-1402, total anti-HER3 antibody, and MAAA-1181a.
- 2. To evaluate efficacy of U3-1402.
- 3. To assess the incidence of human anti-drug antibodies (ADAs) against U3-1402.

### 2.1.2.2. Dose Finding and Dose Expansion Parts

The secondary objective is as follows:

- 1. To assess the PK profiles of U3-1402, total anti-HER3 antibody, and MAAA-1181a.
- 2. To assess the incidence of ADA against U3-1402.

### 2.1.2.3. Dose Expansion Part

1. To determine the relationship between efficacy of U3-1402 and HER3 expression.

### 2.1.3. Exploratory Objectives

The exploratory objectives for the Dose Escalation Part, Dose Finding Part, and Dose Expansion Part are as follows:

- 1. To explore the concentration-corrected QT (QTc) relationships of U3-1402, total anti-HER3 antibody, and MAAA-1181a.
- 2. To identify biomarkers that correlate with U3-1402 response or toxicity.

## 2.2. Study Hypotheses

U3-1402 will have anticancer activity in breast cancer patients whose tumors express HER3 and will be well-tolerated with acceptable PK properties.

# 2.3. Study Endpoints

The endpoints for the study include the following:

• Pharmacokinetic endpoints:

Serum PK endpoints (area under the concentration-versus-time curve, from time 0 to the last measurable concentration as calculated by the linear-up log-down trapezoidal method [AUClast], AUC during dosing interval [AUCtau], Cmax, time of maximum observed concentration [Tmax] and trough serum concentrations [Ctrough]) of U3-1402 for each subject will be estimated using standard noncompartmental methods. For total anti-HER3 antibody and MAAA-1181a, all parameters listed above will be estimated.

### • Safety endpoints:

Safety endpoints will include dose-limiting toxicities (DLTs), serious adverse events (SAEs), treatment-emergent adverse events (TEAEs), adverse events of special interest (AESIs), physical examination findings (including ECOG PS), vital sign measurements, standard clinical laboratory parameters, electrocardiogram (ECG) parameters, echocardiography (ECHO)/multiple gated acquisition scan (MUGA) findings and ophthalmologic findings.

### • Efficacy endpoints:

Tumor response will be evaluated using Response Evaluation Criteria in Solid Tumors (RECIST) version 1.1. Objective response rate (ORR) (the sum of complete response [CR] rate and partial response [PR] rate), disease control rate (DCR) (the sum of CR rate, PR rate, and stable disease [SD] rate), duration of response (DOR), clinical benefit rate (CBR; the proportion of subjects who achieved a best overall response of CR or PR or  $SD \ge 6$  months), time to response (TTR), PFS, OS, and percent change in target lesion(s).

### 3. STUDY DESIGN

## 3.1. Overall Design

#### **3.1.1. Overview**

### **3.1.1.1. Study Type**

This is a Phase 1/2, multicenter, open-label, multiple dose, first-in-human study of U3-1402 in subjects with HER3-positive metastatic breast cancer. The Dose Escalation and Dose Finding Parts will be conducted in Japan only. The Dose Expansion Part may include subjects from any participating country, including the US and Japan.

### 3.1.1.2. Treatment Groups

#### **Dose Escalation Part**

In the Dose Escalation Part, eligible subjects with HER3-high breast cancer who have been refractory to or intolerant to standard treatment, or for whom standard treatment is no longer available, will be enrolled. Subjects will receive U3-1402 at varying dose levels based on their assigned cohort to identify the MTD of U3-1402. Refer to Section 3.1.3 for further details.

### **Dose Finding Part**

In the Dose Finding Part, eligible subjects with HER3-high breast cancer will be enrolled. Cohorts with multiple drug doses and/or administration schedules, including up-titration of dose, will be selected by the Sponsor for further evaluation. Doses evaluated for alternative administration schedules, including up-titration of dose, will be equal to or less than the MTD (or highest dose evaluated) of U3-1402 administered via IV infusion Q3W. Refer to Section 3.1.4 for details.

#### **Dose Expansion Part**

In the Dose Expansion Part, eligible subjects with HER3-positive (HER3-high or HER3-low), HER2-negative, HR-positive breast cancer who have received ≥2 and ≤6 prior chemotherapy regimens for breast cancer (including ≥2 regimens administered for the treatment of advanced/unresectable or metastatic disease) and those with HER3-high, TNBC who have received 1 to 2 prior chemotherapy regimens in the advanced disease setting will be enrolled to evaluate safety and efficacy of U3-1402 at the RDEs. In the Dose Expansion Part, multiple expansion cohorts will be evaluated as described in Section 3.1.5.

#### 3.1.1.3. Duration of the Study

This study is expected to last approximately 7 years from the time the first subject is enrolled to the time the last subject is off the study. The end of the study is defined as the date of completion of the last visit or procedure shown in the Schedule of Events (Section 17.8) in the trial globally.

Sponsor may terminate the study at any time due to administrative reason or at request from competent regulatory authorities.

## 3.1.1.4. Duration of Subject Participation

The number of treatment cycles is not limited in this study. Subjects will continue study treatment until withdrawal of consent, progressive disease (PD), unacceptable toxicity, death, or termination of the study by Sponsor.

There is an end-of-treatment (EOT) Visit which occurs within 7 days after the date of discontinuation. A 28-Day F/U Visit (- 7 days) takes place 28 days after the last U3-1402 administration. If the subject begins another anticancer therapy before the end of the 28 days (- 7 days), every effort will be made to complete all of the F/U assessments prior to starting the new therapy. For further details concerning assessments performed at the EOT and F/U Visits refer to Section 6.7 and Section 6.8, respectively.

For subjects with positive ADA at F/U visit (or EOT visit if F/U visit was not performed), additional serum ADA samples should be collected every 3 months (± 1 month) for up to 1 year after the last dose of U3-1402, unless one of the following occurs sooner; the ADA becomes negative; the ADA titer falls below baseline if ADA was measurable prior to first dose of U3-1402; the subject starts another therapy for cancer; or the subject withdraws consent from the study.

After discontinuation from study treatment, follow-up information for survival and subsequent anticancer therapy, if available, should be collected approximately every 3 months; refer to Section 6.9 for details.

#### 3.1.2. Dose Escalation Process and Dose Selection

The study will enroll subjects into cohorts during dose escalation by modified continuous reassessment method (mCRM) with escalation with overdose control (EWOC) principle as outlined in Section 3.1.3). The starting dose will be 1.6 mg/kg (see Section 3.2.1 for justification of the human starting dose).

In the Dose Escalation Part, the second subject in each dosing level should start dosing at least 24 hours after the initial dosing of the first subject to check the acute toxicity such as infusion-related reaction.

In the Dose Finding Part, subjects will be enrolled to multiple Dose Finding cohorts equal to or less than the MTD (if attained, or the highest dose evaluated) to determine the RDEs (Section 3.1.4). Doses evaluated for alternative administration schedules, including up-titration of dose, will be equal to or less than the MTD (or highest dose evaluated) of U3-1402 administered via IV infusion Q3W.

In the Dose Expansion Part, subjects will be enrolled to multiple Dose Expansion cohorts as described in Section 3.1.5.

#### 3.1.3. Dose Escalation Part

Dose escalation of U3-1402 to determine the MTD will be guided by the mCRM using a Bayesian logistic regression model (BLRM) following EWOC principle. The proposed human starting dose of U3-1402 is 1.6 mg/kg, based on 1/6 human equivalent dose (HED) of HNSTD in monkey (30 mg/kg). The following planned dose levels will be assessed in the Dose Escalation Part (Table 3.1). U3-1402 will be administered via IV infusion Q3W in 21-day cycles in the Dose Escalation Part.

**Table 3.1: Dose Escalation Cohorts** 

Dose Cohort a	U3-1402 Dosage (21-day cycles)
1	1.6 mg/kg IV infusion Q3W
2	3.2 mg/kg IV infusion Q3W
3	4.8 mg/kg IV infusion Q3W
4	6.4 mg/kg IV infusion Q3W
5	8.0 mg/kg IV infusion Q3W
6	9.6 mg/kg IV infusion Q3W

IV = intravenous; Q3W = once every 3 weeks

#### Dose level increment during Dose Escalation Part by mCRM with EWOC

• The dose level increment should be no more than 100% even if the model suggests a higher dose than 100% for the next cohort.

The escalation by mCRM with EWOC principle will be based on a BLRM. The logistic regression model for the dose-response (DLT rate) relationships will include 2 parameters, the intercept, and slope. After at least 3 subjects of each cohort complete DLT evaluation during Cycle 1, posterior distributions of DLT rate are derived for all dose levels based on the BLRM using DLT outcome data from all assessed doses and a pre-specified prior distribution for the model parameters. The posterior probability of DLT rate in the following 4 intervals at each dose level: 0% ≤DLT rate ≤16% as DLT rate interval for under-dosing, 16% <DLT rate ≤33% as target DLT rate interval, 33% <DLT rate ≤60% as DLT rate interval for excessive toxicity, and 60% <DLT rate ≤100% as DLT rate interval for unacceptable toxicity will then be calculated, and used for dose recommendation for the next cohort according to the EWOC principle. The EWOC principle requires that the mCRM recommended dose for the next cohort of subjects is the one with the highest posterior probability of the DLT rate in the target DLT rate interval of 16% <DLT rate ≤33% among all doses fulfilling the overdose control constraint: there is less than 25% of probability for DLT rate >33% (probability for excessive or unacceptable toxicity).

The dose for the next cohort will be chosen by the Sponsor based on the dose recommendation by the mCRM, clinical assessment of toxicity profiles, and PK information observed thus far.

Cohorts of at least 3 DLT evaluable subjects will be enrolled and assessed for DLT during the dose escalation process. As an exception, the model will be reevaluated before enrollment of any additional subjects to the cohort if 2 DLT evaluable subjects in the cohort experience DLT before the enrollment of the third subject. Enrollment of subjects to a new higher dose cohort requires completion of DLT evaluation of at least 3 subjects treated in the current cohort. Subjects who have neither completed DLT evaluation nor experienced DLT will be censored and not included in the BLRM update. In the event when subjects in the previous cohort experience DLTs after enrollment of subjects to a new cohort has begun, dose level assignment of the next

<sup>a Additional dose levels may also be considered based on review of available safety, tolerability, and pharmacokinetic data in this and other studies with the investigational agent.

subject in the new cohort will be based on an updated BLRM using DLT outcome data from all assessed doses. Subject ongoing will continue treatment at their assigned dose level.

Subjects can be backfilled (added) to lower doses previously proven to be safe at any point during dose escalation.

To better understand the safety, tolerability, PK or preliminary activity of U3-1402, additional patients may be enrolled to preceding dose levels, or to intermediate dose level before or while proceeding with further dose escalation.

The Dose Escalation Part will be stopped according to the following rules:

- i. at least 6 evaluable subjects have been enrolled at the MTD level with at least 18 evaluable subjects in total enrolled in the Dose Escalation Part
- ii. at least 9 evaluable subjects have been enrolled at a particular dose level, the model recommends continuing at the same dose level, and the posterior probability of the DLT rate falling within the target DLT interval is ≥50%. The target DLT interval is defined as 16% <DLT rate ≤33%
- iii. DLT assessment with at least 3 evaluable subjects at the maximum possible dose level with upper limit of 95% credible interval for posterior probability of DLT rate is lower than 33%
- iv. the initial dose level is too toxic.

Cohorts may be expanded at any dose level or at the MTD for further elaboration of safety, or PK parameters as required.

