#### 1.2.3. Clinical Experience

This is a first-in-human study of U3-1402.

As of the 25 Aug 2018 data cut-off, 56 subjects had received U3-1402 as part of Study U31402-A-J101: 34 subjects in the Dose Escalation Part, 8 subjects in the Dose Finding Part, and 14 subjects in the Dose Expansion Part. At the time of the data cut-off, 41 subjects were receiving treatment, 13 subjects had discontinued treatment due to disease progression, 1 subject had discontinued treatment due to Grade 2 pneumonitis, and 1 subject had withdrawn consent.

Fifty-four (96.4%) of the 56 treated subjects had experienced at least 1 TEAE. All 54 subjects had also experienced at least 1 TEAE considered by the investigator as related to study drug. Among all treated subjects, the most frequent (>20%) TEAEs, all grades, regardless of causality

and noted in descending order of frequency, included nausea (47 subjects [83.9%]), decreased appetite (36 subjects [64.3%]), platelet count decreased (36 subjects [64.3%]), white blood cell count decreased (30 subjects [53.6%]), neutrophil count decreased (29 subjects [51.8%]), vomiting (25 subjects [44.6%]), aspartate aminotransferase (AST) increased (23 subjects [41.1%]), alanine aminotransferase (ALT) increased (22 subjects [39.3%]), anemia (19 subjects [33.9%]), stomatitis (17 subjects [30.4%]), alopecia (15 subjects [26.8%]), diarrhea (15 subjects [26.8%]), fatigue (12 subjects [21.4%]), and malaise (12 subjects [21.4%]).

Eighteen (32.1%) of the 56 treated subjects had developed treatment-emergent SAEs, including 12 subjects (21.4%) with study drug-related SAEs. The treatment-emergent SAEs, in descending order of frequency, included platelet count decreased (6 subjects [10.7%]); decreased appetite (3 subjects [5.4%]); and atelectasis, cellulitis, cholecystitis acute, dehydration, dyspnea, implant site infection, malaise, myalgia, pneumonia, pneumothorax, pseudomembranous colitis, thrombocytopenia, and urinary tract infection (1 subject [1.8%] each).

Additional data describing the clinical experience of U3-1402 are available in the current Investigator's Brochure.

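### No model re-evaluation is specified when a cohort's second DLT comes after the third subject is enrolled, so enrolment can stay open at a level that fails the 25% overdose limit

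*Combined protocol and SAP*

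**What the plan says.** All references are to the combined protocol and SAP.

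- **Routine update (Section 3.1.3).** "After at least 3 subjects of each cohort complete DLT evaluation during Cycle 1, posterior distributions of DLT rate are derived" and used to recommend a dose for the next cohort. The recommended dose must have less than a 25% probability of a DLT rate above 33%.
- **Cohort size (Section 3.1.3).** "Cohorts of at least 3 DLT evaluable subjects will be enrolled"; no maximum is given. Later in the section: "Cohorts may be expanded at any dose level or at the MTD".
- **The one in-cohort exception (Section 3.1.3).** "the model will be reevaluated before enrollment of any additional subjects to the cohort", but only "if 2 DLT evaluable subjects in the cohort experience DLT before the enrollment of the third subject".
- **Other protections (Section 3.1.3).** Three completed evaluations are needed before a higher dose opens. If DLTs appear in a previous cohort after a new one has started, the next assignment in the new cohort uses an updated model. Subjects still under evaluation without a DLT are left out of an update.
- **Spacing (Section 3.1.2).** "the second subject in each dosing level should start dosing at least 24 hours after the initial dosing of the first subject". No interval is given for the third subject onward.

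**The concern.** The exception accepts that two early DLTs justify rerunning the model before more subjects join. It then makes this depend on something unrelated to toxicity, namely whether the third subject has been enrolled. Once that has happened the exception can no longer apply. The higher-dose gate does not govern enrolment at the same dose, and the late-DLT update concerns a new cohort following a previous one.

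That leaves one uncovered interval, from the third enrolment to the routine update, in a cohort that takes more than three subjects. A second DLT in that interval triggers nothing in the text, and a fourth or later subject may enter at the same level. The faster the enrolment, the less the exception protects. At stake is whether subjects can be added at a level that the protocol's own model, if run on the data in hand, would not recommend.

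**Working it through.** **1. Inputs.** Sections 11.7.1 and 11.7.2 give the model logit π(d) = log α + β log(d/9.7). The prior for (log α, log β) is bivariate normal with means (−1.0981, −0.4913), standard deviations (2.0445, 0.8677) and correlation −0.3317. Dose levels come from Table 3.1. The limit is P(DLT rate > 33%) < 0.25.

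**2. Reproducing the plan's figure.** At 9.7 mg/kg the log-dose term is zero, so the prior median is 1/(1 + e^1.0981) = 25.0%. At 1.6 mg/kg, numerical integration gives 8.1%. Section 11.7.2 states approximately 24.5% and 8.0%, so the printed prior behaves as described.

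**3. Posterior at the current level.** The likelihood is the product of π^x(1 − π)^(n − x) over the doses tested, integrated on a grid. The count 2/2 is what the model sees while the third subject is pending and left out. The count 2/3 is two DLTs plus one subject who has finished without one. Entries are P(DLT rate > 33%).

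| Current level, mg/kg | 2/2, lower levels 0/3 | 2/3, lower levels 0/3 | 2/2, 1/3 just below | 2/3, 1/3 just below |
|---|---|---|---|---|
| 1.6 | 0.91 | 0.78 | – | – |
| 3.2 | 0.59 | 0.47 | 0.87 | 0.78 |
| 4.8 | 0.38 | 0.29 | 0.68 | 0.58 |
| 6.4 | 0.27 | 0.20 | 0.53 | 0.44 |
| 8.0 | 0.21 | 0.15 | 0.45 | 0.36 |
| 9.6 | 0.19 | 0.14 | 0.41 | 0.32 |

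In the last two columns, levels further down are 0/3.

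**4. Dependence on earlier data.**
- With 0/6 at each lower level, 2/3 gives 0.264 at 3.2 and 0.110 at 4.8.
- With 0/3 at 1.6 and 3.2 and 4.8 skipped, 2/3 at 6.4 gives 0.374.
- With 1/3 at 1.6, the model already puts 3.2 at 0.47 before anyone is treated there. The 3.2 entries in the last two columns are therefore correct posteriors, but the model alone would not lead there from that count. For 4.8 to 9.6 the corresponding values before treatment are 0.24, 0.14, 0.10 and 0.08, so those levels can be reached.

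**5. How often the exception can apply.** Accrual and DLT timing are not given. As an assumption, take equal enrolment gaps of g days, DLT times uniform over the 21-day window, and DLT rate p. Subject 1 has been observed for 2g days and subject 2 for g days when subject 3 enrols, so

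P(exception) = p² × min(1, 2g/21) × min(1, g/21), which cannot exceed p².

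P(at least 2 DLTs in 3) = 3p²(1 − p) + p³. At p = 0.33 this is 0.2189 + 0.0359 = 0.2548.

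| g, days | P(exception), p = 0.33 | Share of cohorts with ≥2 DLTs in 3 |
|---|---|---|
| 1 | 0.1089 × 2/21 × 1/21 = 0.0005 | 0.2% |
| 7 | 0.1089 × 14/21 × 7/21 = 0.0242 | 9.5% |
| 14 | 0.1089 × 1 × 14/21 = 0.0726 | 28.5% |
| 21 or more | 0.1089 | 42.7% |

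With fully sequential enrolment the share is 0.0256/0.0686 = 37% at p = 0.16 and 0.36/0.648 = 56% at p = 0.60.

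**The case against.** The strongest reply is that nothing in the plan is breached. Sections 3.1.3 and 11.7.3 apply the 25% limit to the dose recommended for the next cohort and do not promise a check before each subject. This stands: the point is a gap in a design choice, not a failure of the stated limit or a contradiction in its definition.

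Four stronger readings are tempting, and the documents do not support them.

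- **The exception almost never applies.** This needs an accrual rate the documents do not give. Some DLTs in Section 3.1.7 need more than 7 days, or at least 14, to be met, but others have no minimum duration. With near-sequential enrolment the exception would apply in up to 10.9% of cohorts at a 33% DLT rate and 36% at 60%.
- **Two DLTs always put the level over the limit.** With 0/3 at every lower level, 2/3 passes at 6.4, 8.0 and 9.6, and 2/2 passes at 8.0 and 9.6.
- **Subjects were in fact exposed this way.** Section 1.2.3 reports "34 subjects in the Dose Escalation Part", and 34/6 = 5.7 per planned level. That average mixes expansion and backfilling, which may follow a model run, so it shows only that larger cohorts are plausible.
- **Every cohort is affected.** A cohort of exactly three has no later subject, and backfilling goes only to lower doses already judged safe.

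Inpatient stay through Day 21 of Cycle 1 (Section 6.2), consultation on DLTs (Section 3.1.7) and regular safety review (Section 3.1.8) reduce the risk, but none requires the model to be rerun. Escalation enrolment was also probably over well before Version 9.0: 14 expansion subjects had been treated by August 2018. That lowers the practical benefit but leaves the gap in the text.

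**Conclusion.** The concern holds in limited form. The text is silent on a second DLT that occurs after the third enrolment and before the routine update, and unlimited cohort size makes a fourth enrolment in that interval possible.

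On the printed prior with clean lower cohorts of three, such a subject could enter at a level failing the limit after 2/2 at 1.6 to 6.4 mg/kg or after 2/3 at 1.6 to 4.8. After 1/3 at the level just below, both counts fail at every level from 3.2 to 9.6, with the caveat about reaching 3.2 noted in the working. The excess ranges from slight (0.27 after 2/2 at 6.4) to large (0.91 after 2/2 at 1.6).

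The 2/3 figures matter inside the interval only if a subject with a DLT is not yet counted as having completed evaluation; otherwise three outcomes are in and the routine update is due. The 2/2 figures do not depend on that reading. The frequency cannot be stated without accrual. Under the timing assumption at a 33% DLT rate, the exception misses more than half of cohorts with at least two DLTs in three, even with sequential enrolment.

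**What to change.** Reconcile the two-DLT exception and the late-DLT update in Section 3.1.3 with the EWOC principle there and in Section 11.7.3. The model re-evaluation that the protocol already requires before further enrolment to the cohort should not depend on whether the third subject happens to be enrolled. The action stays the protocol's own; no dose, dosing hold or stopping rule is proposed here.

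The change is a short edit to Section 3.1.3. Its operational cost is at most a brief enrolment pause while an existing model is rerun. If escalation enrolment has closed, the edit matters only for further escalation cohorts or the additional dose levels that the Table 3.1 footnote allows.
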